9.6. Data management

All analyses will be conducted using Statistical Analysis System (SAS) version 9.4 (SAS Institute Inc., Cary, North Carolina) and SAS Enterprise Guide 6.1 or later. The data will be extracted from the ORD once per report. The annual interim reports will include the structured ORD data only. The final report will additionally incorporate the adjudication results, as described in Section 9.3.1.3.

The following sections of the protocol (Sections 9.6.1 and 9.6.2) pertain to the data collected for the review of medical charts described in Section 9.3.1.3.

9.6.1. Data collection tools (DCTs)

As used in this protocol, the term DCT should be understood to refer to either a paper form or an electronic data record or both, depending on the data collection method used in this study.

A DCT is required and should be completed for each included patient for whom outcomes are being adjudicated via medical record review. The completed original DCTs are maintained by Optum and should not be made available in any form to third parties, except for appropriate regulatory authorities, without written permission from Pfizer. Optum shall ensure that the DCTs are securely stored at the study site in encrypted electronic form and will be password protected to prevent access by unauthorized third parties.

Optum has ultimate responsibility for the collection and reporting of all clinical, safety, and laboratory data entered on the DCTs and any other data collection forms (source documents)

and ensuring that they are accurate, authentic/original, attributable, complete, consistent, legible, timely (contemporaneous), enduring, and available when required. The DCTs are completed and submitted by the clinician reviewer(s), with time, date, and name of the clinician reviewer(s) recorded, who by submitting the DCTs attest to their accuracy and completeness. Any corrections to entries made in the DCTs or source documents must be dated, initialed, and explained (if necessary) and all prior entries are maintained for documentation.

The source documents are the hospital or the physician's chart. In these cases, data collected on the DCTs must match those charts.

9.6.2. Record retention

To enable evaluations and/or inspections/audits from regulatory authorities or Pfizer, Optum agrees to keep all study-related records, including sufficient information to link records, (eg, DCTs and hospital records), electronic copies of all DCTs, safety reporting forms, source documents, and adequate documentation of relevant correspondence (eg, letters, meeting minutes, and telephone call reports). The records should be retained by Optum according to local regulations or as specified in the Optum contract, whichever is longer. Optum must ensure that the records continue to be stored securely for so long as they are retained.

If Optum becomes unable for any reason to continue to retain study records for the required period, Pfizer should be prospectively notified, and study records should be retained under an arrangement acceptable to Pfizer that protects the confidentiality of the records (eg, secure off-site storage). Study records must be kept for a minimum of 15 years after completion or discontinuation of the study, unless Optum and Pfizer have expressly agreed to a different period of retention via a separate written agreement.

If Pfizer would like the Study Records kept longer than the 15-year retention period, Pfizer will notify Optum prior to the end of the 15-year retention period.

9.7. Data analysis

Detailed methodology for summary and statistical analyses of data collected in this study will be documented in an SAP, which will be dated, filed, and maintained by Pfizer. The SAP may modify the plans outlined in the protocol; any major modifications of primary endpoint definitions or their analyses be reflected in a protocol amendment.

9.7.1. Annual interim reports

For each annual interim report, Optum will identify the number of pregnancies that are accrued into each of the exposure cohorts by exposure window. Eligible pregnancies included in each of the study cohorts will be described with respect to demographic characteristics (age at the ECD, geographic region, etc.), year of cohort entry, select comorbidities, and COVID-19 characteristics during pregnancy (eg, number of COVID-19 episodes, hospitalization during COVID-19 episode, etc.). Interim reports 2-4 will include information on all pre-specified covariates. Flow charts describing attrition due to application

of inclusion and exclusion criteria, including exclusion due to receipt of cohort medications in an inpatient setting, will be included. Interim reports will also include a tabulation of claims-based outcomes, by cohort and exposure window. The number of claims-identified outcomes available for medical record request will also be indicated.

Outcome validation via medical record review will not be performed until the final analysis. By design, for study outcomes which will be validated via medical record review, the initial claims definitions will be highly sensitive to ensure that all potential events are captured and subsequently reviewed by clinicians. For this reason, it is expected that annual interim reports will overestimate the number of outcome events occurring in study cohorts. Interim reports 2-4 will therefore include an alternative definition of MCM (MCM2) using only ICD-10-CM codes associated with major malformations as defined by the New York State Department of Health (New York State Department of Health 2023). Pending results from interim reports, the claims algorithm used to identify potential MCMs for medical record confirmation may be modified prior to implementation of final analyses. In that case, the protocol and SAP will be amended prior to implementation of final analyses to specify the claims algorithm used for medical record confirmation.

Interim reports 2-4 will also include estimates of effective sample size using the estimated ATT weights described by Shook-Sa and Hudgens (Shook-Sa & Hudgens 2022).

The number of accrued pregnancies will be assessed following the third interim report to determine whether there will be sufficient statistical power to detect a difference in risk across the study cohorts with respect to the outcomes of interest. The study accrual period may be shortened if a sufficient number of pregnancies are accrued prior to the end of the proposed study accrual period. In the event that the accrual of PAXLOVID-exposed pregnancies is slower than expected, the extension of the accrual period and/or the addition of a data partner may be considered.

9.7.2. Final report

For the final report at the culmination of the study, the number of pregnancies with COVID-19 that are accrued into each of the exposure cohorts by exposure window will be reported. Eligible pregnancies included in each of the study cohorts will be described with respect to covariates (Section 9.3.3).

A flow chart depicting the number of pregnant women with COVID-19, pregnancies included in each study cohort, adverse pregnancy outcomes (as identified by claims), livebirths, linked infants, and infant outcomes (as identified by claims) will be provided in the final report. For each outcome confirmed by medical record review, the number of outcomes identified by claims will be reported as well as the subset eligible for medical record request, the subset with medical records retrieved, the subset with confirmed outcomes, and the PPV. Analyses describing the characteristics of medical-record eligible and ineligible pregnancy episodes and pregnancies resulting in a livebirth with linked and non-linked infants will be performed. Multi-gestation pregnancies will be described and sensitivity analyses may restrict to singleton pregnancies for specific outcomes.

The prevalence of pregnancy outcomes and infant outcomes will be described for each cohort separately. Pending sufficient sample size, comparative analyses will be undertaken for each of the pregnancy and infant outcomes comparing the PAXLOVID-exposed pregnancy cohorts (Cohort 1) to the comparator pregnancy cohorts separately (Cohorts 2 and 3), by exposure window.

9.7.2.1. Propensity score modeling

For the final analysis, each pregnancy will be assigned a propensity score, a measure of the probability of receiving PAXLOVID versus a comparator treatment (or no treatment), given the patient's baseline characteristics. This propensity score will be utilized to implement IPTW to adjust for confounding.

IPTW produces groups (after weighting) that have similar patterns of the presence or absence of a large number of factors. The key to propensity score estimation is to perform a rich statistical analysis of the predictors of PAXLOVID exposure. The propensity score logistic regression model can incorporate demographic, comorbidity, treatment history, predictors of treatment choice, and co-medication indicators, as well as other potential confounders and risk factors.

In this study, all of the propensity score model variables will be determined from claims data and will be determined without respect to outcome status. For a given covariate pattern, the propensity score is the fitted value of the probability of being a member of the PAXLOVID group, given membership in the study population and the covariate pattern. To the extent that the decision to be dispensed PAXLOVID depends on the health characteristics of the patient at the time of the decision, the propensity score models the clinical decision-making process.

Four sets of propensity scores will be created: 1 for each of the comparator cohorts (Cohorts 2 and 3) versus Cohort 1, and 1 for each of the exposure windows (first trimester, full pregnancy). The decision to include variables in the model will be based on *a priori* knowledge (eg, expected confounder or known risk factor of adverse pregnancy/infant outcomes).

The covariates listed in Section 9.3.3.2.1 will be considered for inclusion in the model as independent (predictor) variables. The propensity score model will only include covariate information during the baseline period (prior to and including the index date). Hence, the propensity scores will incorporate characteristics at the start of the pregnancy. In addition to the pre-specified variables in Section 9.3.3.2.1, the most common diagnoses, procedures, and medications observed prior to estimated date of conception will be evaluated to ensure no important confounders are missed.

If there are too many variables given the number of pregnancies exposed to PAXLOVID (eg, < 10 exposed pregnancies for every variable in the propensity score model), the number of variables may be reduced using a LASSO model. Variables with an estimate of 0 in the LASSO model will be dropped from the propensity score variable list and a logistic regression model will be run using the remaining variables. For variable pairs that are highly correlated (eg, correlation coefficient > 0.9), 1 may be eliminated.

As patterns of prescribing tend to change over time, particularly for newly available products, with early adopters of the formulation (both physician and patient) tending to differ from late adopters, prediction equations need to account for these secular changes. As such, the propensity score models will incorporate calendar time to take into account the changing nature of the patient pool and COVID treatment guidelines over time. Incorporating calendar time may also account for changes in COVID-19 variants and severity over time (eg, Delta versus Omicron).

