9.2.6.2. Cohort 2: Treated comparator only cohorts

Pregnancies will be included in the Treated Comparator Only cohorts (Cohort 2) if they meet the following criteria:

- 1. Any of the following:
 - a. Administration of remdesivir in an outpatient setting between 9 days prior to ECD and the end of the exposure window.

OR

b. Administration of bebtelovimab in an outpatient setting between 60 days prior to ECD and the end of the exposure window.

AND

2. No dispensing of PAXLOVID (any setting) between 12 days prior to first eligible comparator drug dispensing and the end of the exposure window.

The 9-day pre-ECD window for remdesivir was chosen because of the 3-day recommended treatment course and 6 days to achieve 5x the clearance half-life (FDA 2022b). The 60-day pre-ECD window for bebtelovimab was chosen because of the 60-day requirement to achieve 5x the clearance half-life (FDA 2022c).

Pregnancies with exposure to more than 1 Cohort 2 medication (eg, a pregnancy exposed to both remdesivir and bebtelovimab, or other future approved or authorized COVID-19 therapies included in Cohort 2) will be eligible for inclusion.

Lists of approved or authorized COVID-19 therapies for the definition of the treated comparator will be periodically reviewed and updated in the SAP as necessary.

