9.2.6.3. Cohort 3: Untreated comparator cohorts

Pregnancies will be included in the Untreated Comparator cohorts (Cohort 3) if they meet the following criteria:

1. At least 1 COVID-19 diagnosis (ICD-10 U07.1) in an outpatient, inpatient, or emergency room setting between 7 days prior to ECD and the end of the exposure window.

AND

- 2. No exposure to any authorized COVID-19 therapies, regardless of setting (ie, outpatient/inpatient). Authorized therapies used to exclude pregnancies from the unexposed cohorts include:
 - a. Study cohort drugs
 - b. Other approved or authorized treatments (eg, molnupiravir, other monoclonal antibodies)
 - c. Convalescent plasma (indicated for patients with immunosuppressive disease or receiving immunosuppressive treatment)

Lists of authorized COVID-19 therapies for the exclusion definition of the untreated comparator cohort will be periodically reviewed for completeness and updated in the SAP as necessary and will include all approved or authorized (EUA for the treatment of mild-to-moderate COVID-19) medications at any point during the study period. Medication-specific pre-ECD windows for exclusion for other monoclonal antibodies and convalescent plasma will be based on typical treatment durations and medication half-lives (as with other study cohort treatments) and defined in the SAP.

9.2.7. The index date for Cohort 3 will be the date of COVID-19 diagnosis plus the treatment interval (the median interval between COVID-19 diagnosis and treatment in Cohort 1; as defined in Section 4.3.3.1.1 in the SAP)Follow-up

For the assessment of pregnancy outcomes, follow-up for each pregnant woman will extend from the day following cohort entry (ECD) until the earliest of: disenrollment from the health plan, end of the pregnancy, or 01 September 2026.

For the assessment of infant outcomes, linked infants (the subset of pregnancies resulting in livebirths that are linked to the mother's data) will be followed from the date of delivery until the earliest of: disenrollment from the health plan or 1 year of age.

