9.3.2. Study drug exposures

9.3.2.1. Cohort 1: PAXLOVID exposure

Exposure to PAXLOVID will be identified through the presence of NDCs on pharmacy dispensing claims:

- 00069034506
- 00069034530

- 00069108506
- 00069108530
- 00069110104
- 00069110120

Codes will be periodically reviewed for completeness and updated as necessary.

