9.3.2.2. Cohort 2: Treated comparator only exposures

Exposure to remdesivir and bebtelovimab will be identified through the presence of drug administration codes (HCPCS):

- J0248 Injection, remdesivir, 1 mg
- Q0222 Injection, bebtelovimab, 175 mg
- M0222 Intravenous injection, bebtelovimab, includes injection and post administration monitoring
- M0223 Intravenous injection, bebtelovimab, includes injection and post administration monitoring in the home or residence; this includes a beneficiary's home that has been made provider-based to the hospital during the COVID-19 public health emergency

Codes will be periodically reviewed for completeness and updated in the SAP as necessary.

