9.3.3. Covariates

9.3.3.1. Time periods

[figure not shown]
The following dates and time periods will be used (Figure 4):

- Index date the date of start of treatment (Cohorts 1 and 2) or COVID-19 diagnosis plus the treatment interval (Cohort 3)
- Baseline the 6 months prior to ECD through the index date, with potential variability in capture of time prior to EDC according to timing of treatment and COVID-19 diagnosis as described below. As an example, each patient with the same timing of an index exposure (eg, treatment/COVID-19 at Day 60 of pregnancy) will have the same amount of baseline, but by anchoring to treatment/COVID-19, there is

potential for variability in the baseline window length according to the timing of treatment or COVID-19 infection.

- For individuals with index dates during pregnancy, the baseline period includes the ECD (Figure 4A)
- o For individuals index dates prior to ECD (eg, PAXLOVID initiation 2 days prior to ECD), the baseline period ends prior to ECD (Figure 4B)
 - For these pregnancies, select characteristics at ECD will still be captured (ie, maternal age at ECD, calendar year of ECD)
- All available pre-pregnancy data all available data from 01 January 2016 onward
- First trimester/pregnancy the time between ECD and end of first trimester/end of pregnancy

Figure 4. Time Periods for the Assessment of Covariates.

The baseline window will be defined using the first eligible treatment or COVID-19 diagnosis during an exposure window. Descriptive characteristics that capture the total number of COVID-19 therapies (eg, multiple courses of PAXLOVID) will be described during the first trimester/pregnancy window.

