9.3.3.2.1. Baseline covariates

- Demographics including age, geographic area, and month and year of ECD (at the time of ECD)
- Healthcare utilization
 - Length of health plan enrollment
 - Number of physician visits, emergency room visits, and hospitalizations (prior to and during pregnancy, separately)
- Vaccinations received (eg, Tdap)
- Diagnoses related to alcohol, recreational drug, and tobacco use
- Diagnoses associated with increased risk for evolution to severe COVID-19, and the subset with evidence of treatment (for select comorbidities)
- Diagnoses associated with increased risk for thromboembolic events
- Diagnoses related to contraindications for study drugs, including renal and hepatic impairment
- Receipt of medications listed as contraindications for study drugs, including drugs highly dependent on CYP3A for clearance and drugs with established or potentially significant interactions with PAXLOVID
- Receipt of COVID-19 vaccines through drug or procedure codes (Wong et al. 2022) (using all available pre-pregnancy data)
 - o Time since most recent COVID-19 vaccination
- Diagnoses associated with an increased incidence of the pregnancy outcomes such as prior history of pregnancy complications, obesity, hypertension, chronic kidney disease, diabetes, infection during pregnancy, and cardiovascular disease
- Prior COVID-19 (using all available pre-pregnancy data; prior to and during pregnancy, separately)

- Characteristics of COVID-19 episode (up to and including treatment initiation or COVID-19 diagnosis) associated with cohort medication exposure (if applicable), including:
 - Site of diagnosis (eg, inpatient/emergency room)
 - Gestational age at start of COVID-19 episode
 - Time to cohort-defining treatment initiation
 - Receipt of supplemental oxygen
 - Critical care indicators
- Calendar time (month and year) of index date (first COVID-19 treatment initiation or COVID-19 infection)
- Duration between index date and ECD (this value will be positive if the index event occurred after ECD, and negative if the index event occurred prior to ECD)

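### The propensity-score baseline includes the index day, so the drug administration that defines Cohort 2 can be counted as prior healthcare use, while Cohort 1's pharmacy entry adds no visit

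*Protocol*

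**What the plan says.** **Window.** Protocol 9.3.3.1 defines the index date as "the date of start of treatment (Cohorts 1 and 2) or COVID-19 diagnosis plus the treatment interval (Cohort 3", and baseline as "the 6 months prior to ECD through the index date". Section 9.7.2.1 repeats the inclusive endpoint for the propensity score: "The propensity score model will only include covariate information during the baseline period (prior to and including the index date".

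**Covariate.** Section 9.3.3.2.1 lists, among the baseline covariates, "Number of physician visits, emergency room visits, and hospitalizations (prior to and during pregnancy, separately". It makes no exception for the encounter that defines cohort membership.

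**Entry events.**
- Cohort 1 (9.3.2.1): "Exposure to PAXLOVID will be identified through the presence of NDCs on pharmacy dispensing claims". Section 9.2.6.1 requires an outpatient dispensing but neither a visit nor a diagnosis.
- Cohort 2 (9.3.2.2): "Exposure to remdesivir and bebtelovimab will be identified through the presence of drug administration codes". Section 9.2.6.2 requires "Administration of remdesivir in an outpatient setting between 9 days prior to ECD and the end of the exposure window", or the equivalent for bebtelovimab from 60 days before the estimated conception date (ECD).
- Cohort 3 (9.2.6.3): "At least 1 COVID-19 diagnosis (ICD-10 U07.1) in an outpatient, inpatient, or emergency room setting". The index date follows that diagnosis by the treatment interval.

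**Status of the covariates.** Section 9.3.3.2 equates baseline with pre-treatment. Section 9.7.2.1 says the scores describe the pregnancy at its start. Listed covariates are candidates for the model, and their detailed definitions are left to the SAP.

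**The concern.** A window that closes on the treatment day is neither pre-treatment nor a picture of the pregnancy at its start, so the protocol's own statements do not agree. The disagreement matters because the cohorts enter by different kinds of claim. A Cohort 2 pregnancy has, by definition, a medical encounter on its index day. A Cohort 1 pregnancy need only have a pharmacy claim. If the administration counts as a visit, Cohort 2 appears to use more care even when genuine prior use is identical.

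The propensity model would then treat route of entry as a confounder. Weighting brings recorded visits closer together by favouring Cohort 2 pregnancies with fewer genuine visits. If visits go with higher outcome risk, the weighted comparator risk is too low and the prevalence ratio drifts towards apparent harm. The uneven weights also cost effective sample size in Cohort 2, which section 9.5 puts at about one pregnancy for every five exposed to PAXLOVID.

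The planned safeguards work on recorded values. LASSO drops only variables with a zero coefficient, and a spurious predictor of cohort need not have one. The weighted standardized difference can look acceptable while genuine use has become unbalanced. Variables that stay imbalanced may enter the outcome model in their contaminated form.

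**Working it through.** **1. The one relevant figure in the protocol.** Table 3 gives 564 pregnancies with both a COVID-19 code and PAXLOVID, out of 1,021 with PAXLOVID: 564/1,021 = 55.2% (2021: 185/295 = 62.7%; 2022: 379/726 = 52.2%). This agrees with the text's statement that about half were diagnosed. The code may fall at any time in pregnancy, so 55% is only a rough guide to how many of Cohort 1 have a diagnosis visit in baseline.

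**2. Illustration.** From the protocol: Cohort 1 to Cohort 2 at 5:1 (9.5) and weights of 1 for PAXLOVID and e/(1 − e) for comparators (9.7.2.1.1). Assumed:
- Genuine visits are Poisson with the same mean m in both cohorts.
- Every comparator gets one extra entry visit, and a share q of Cohort 1 gets one too.
- The propensity score is logistic in the recorded count alone.
- Outcome risk is multiplied by r for each genuine visit.
- There is no drug effect.
- Cohort 3 is simulated at five comparators per PAXLOVID pregnancy.

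One quantity needs simulation: d, the genuine mean in Cohort 1 minus the weighted genuine mean in the comparator. Because e/(1 − e) is exponential in the count, the rest follows:
- Raw standardized difference with q = 0: −1/√m
- Comparator effective sample size share: exp(−d²/m)
- Spurious prevalence ratio: exp[(r − 1)d]

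**3. Cohort 2, q = 0** (simulated values)

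| m | Raw difference | d | Effective share | Ratio, r = 1.05 | Ratio, r = 1.10 |
|---|---|---|---|---|---|
| 1 | −1.00 | 0.999 − 0.438 = 0.56 | 73% | 1.029 | 1.058 |
| 2 | −0.71 | 1.995 − 1.280 = 0.72 | 77% | 1.036 | 1.074 |
| 4 | −0.50 | 3.998 − 3.174 = 0.82 | 84% | 1.043 | 1.086 |
| 8 | −0.35 | 7.995 − 7.075 = 0.92 | 90% | 1.046 | 1.096 |

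Check at m = 2: exp(0.10 × 0.715) = 1.074 and exp(−0.715²/2) = 0.774, as simulated.

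Overdispersed (gamma-Poisson) counts with means 2 and 4 give raw differences of 0.57 and 0.35 in size, effective shares of 87% and 93%, and ratios of about 1.04 (r = 1.05) and 1.07 to 1.09 (r = 1.10).

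**4. Cohort 2, q = 55%.** The ratio falls to 1.015–1.021 (r = 1.05) and 1.029–1.043 (r = 1.10), with an effective share of 92% to 98%.

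**5. Cohort 3.** Visits that Cohort 1 makes before dispensing also fall in baseline, so only the between-cohort difference acts.

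| q | Raw difference | Effective share | Ratio, r = 1.05 | Ratio, r = 1.10 |
|---|---|---|---|---|
| 55% | −0.42 to −0.16 | 86% to 98% | 1.020–1.023 | 1.040–1.046 |
| 80% | −0.20 to −0.08 | 96% to 99% | 1.009–1.010 | 1.019–1.020 |
| 100% | about 0 | 100% | 1.00 | 1.00 |

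**6. With the entry encounter left out everywhere.** Recorded and genuine counts coincide, d = 0, and the artefact disappears.

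**The case against.** The best defence is that the protocol does not finally fix the harm. Covariates are only candidates, and whether an administration code is a physician visit is the kind of definition that belongs in the SAP. That stands, and it makes the size conditional. It does not settle the point, because the protocol itself sets the window and a code list does not move the window's end.

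The illustration is also severe: one covariate, with each visit itself raising risk. If visits instead mark underlying health, and the separately listed pre-pregnancy count (assumed mean 3) is also in the model, the spurious ratio drops to 1.005–1.013 at 5% per visit and 1.01–1.03 at 10%. An effective-sample-size loss of about 10% to 18% remains. Interim reports 2 to 4 would show effective sample size, but not why it fell.

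A reader might infer more than the documents support:
- **That no Cohort 2 pregnancy can have zero visits during pregnancy, so overlap fails.** Section 9.2.6.2 admits remdesivir from 9 days and bebtelovimab from 60 days before ECD, and 9.3.3.1 ends baseline before ECD for such index dates. If the first trimester ends 77 days after ECD (assumed), 60/(60 + 77) = 44% of eligible bebtelovimab days in that window precede ECD.
- **That the Cohort 3 diagnosis visit has no counterpart in Cohort 1.** Table 3 shows that many PAXLOVID pregnancies carry a diagnosis code.
- **That empirically selected diagnoses, procedures and drugs are contaminated in the same way.** Section 9.7.2.1 looks for these before conception.
- **That the ratio reaches 1.16 to 1.21.** This needs a 20% risk increase per visit, for which the protocol gives no source, and a single-covariate model.

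**Conclusion.** The point holds in limited form. The protocol closes the propensity-score window on the index day, lists utilisation counts as baseline covariates, and does not exclude the cohort-defining encounter. If administration claims count as visits, the comparison with Cohort 2 can acquire an artificial imbalance. The resulting bias is modest: about 1.03 to 1.10 for a true null under 5% to 10% risk per visit, with 10% to 27% of Cohort 2's effective sample size lost. Both shrink with index-day visits in Cohort 1 or overdispersed counts, and the ratio also shrinks when other covariates capture health status. For Cohort 3 the shift is about 1.02 to 1.05 at q = 55% and vanishes at q = 100%.

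Visit means, risk per visit and the classification of administration claims are assumptions. The upward direction also assumes that visits go with higher risk. The primary objective, estimating malformation risk within each cohort, does not use these weights. What is exposed is the secondary comparison, which is conditional on sample size. In a safety comparison, a shift towards apparent harm that is this cheap to prevent should be removed.

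**What to change.** In 9.3.3.1 and 9.7.2.1, end the visit, emergency room and hospitalisation counts before the index day, by the same fixed offset from the index date in all three cohorts. The offset must be at least one day and must cover the Cohort 3 treatment interval: if that interval is L days, the last counted day should be no later than L + 1 days before the index date. This leaves out the Cohort 2 administration, the Cohort 3 diagnosis encounter, and Cohort 1 prescribing or diagnosis visits within the offset.

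Two details matter:
- **Index day alone.** Cutting only the index day would miss the Cohort 3 diagnosis whenever L exceeds zero. Cutting at the earlier of index date and diagnosis would drop that visit from all of Cohort 3 but keep earlier-day prescribing visits in uncoded Cohort 1 pregnancies, which can reverse the asymmetry.
- **Choice of offset.** L is a median, so up to half of diagnosed Cohort 1 pregnancies may have a longer interval. An offset somewhat above the minimum is safer.

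Keep the index day for comorbidity diagnoses and the COVID-19 severity proxies. Reconcile the pre-treatment description in 9.3.3.2 and the start-of-pregnancy statement in 9.7.2.1 with the window.

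The cost is a sentence in the protocol and SAP and a date offset in the covariate programs. The downside is that a few genuine visits just before the index date go uncounted.
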